**Figure 1. Grace period and accumulation of medication**

Both scenarios in Figure 1 showcase the same subject having filled three prescriptions (A, B and C) of the index treatment. The “grace period” is set to 90 days. In scenario 1, the 2nd prescription (B) is filled before the initial prescription (A) has run out. In scenario 1, the subject is not allowed to accumulate medication and therefore the subject will discontinue and stop being persistent with medication when the supply from prescription B has run out. In scenario 2, accumulation is allowed enabling filled prescription B to close the gap between B and C so that it is equal to or less than 90 days. The subject is now persistent with medication until the supply from filled prescription C runs out. Hence, both the definition of grace period and allowing for accumulation of medication will affect persistence. To investigate the impact of the length of the grace period a sensitivity analysis with a grace period of 60 and 120 days will be carried out.

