### Time to treatment discontinuation

Time to treatment discontinuation, or persistence, is defined as the difference between the start and end-dates for a treatment episode (accordance with the International Society for Pharmacoeconomics and Outcomes Research (ISPOR) Medication Compliance and Persistence Work Group) regardless of reason for discontinuation. The start date for a treatment episode is defined as the date of first dispensed package and the end date is defined as the date of the last dispensed package with the same ATC code, plus the number of days that package, as well as accumulated medicine (see more details below), is intended to cover. This end date is overruled if there is a new filled prescription of another relevant ATC code or death happens before this, then either of these dates represents the end date. If no end of prescribed supply is recorded, data is censored at latest available date in data.

[figure not shown]
Time to treatment discontinuation will be calculated while allowing for patient accumulation of medicine. The number of days covered by the dispensed volume will be determined based on information in the Summary of Product Characteristics (SPC), the volume of dispensed drug, and for sunitinib in first line also by using the prescriber's dosing instruction on the prescription available in the PDR.

For sunitinib, the treatment is provided in 4 + 2 (or 2 + 1) week cycles, where there is a two-week break in treatment after four weeks of continuous drug intake. Hence, the assumed number of days covered by each filled prescription will be adjusted accordingly (i.e. the 14 or 7 days corresponding to the cycle will be added).

When previously supplied dosing instructions cease to be specified, it is assumed that the daily dosage continues in accordance with the previous treatment pattern. Should there be a completeness issue with the variable containing dose information; the recommended average dose per day according to the SPC for each product will be used instead.

[figure not shown]
For axitinib, the treatment is provided in 4 week cycles, without breaks in between. The analysis relies on data on information relating to dispensed pack size and strength;

PFIZER CONFIDENTIAL

Axitinib is available in pack size of 56 tablets, and in strength 1, 3, 5 and 7 mg. Given the dosing recommendations in SPC, a dispensed pack with the strength 1 mg is assumed to last 14 days, whereas the other packs are assumed to last 28 days.

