Patients will be allowed to have gaps between filled prescriptions, but once such a gap exceeds 90 days (the “grace period”) they will be defined as non-persistent. As the Swedish pharmacy system allows patients to refill prescriptions when two-thirds of the previous refill has been consumed (e.g. after two months of a three-month prescription) patients may accumulate large amounts of medication. To account for that, patients will be permitted to accumulate medication from overlapping prescriptions and use it to cover future gaps between filled prescriptions. Figure 1 depicts the effect the grace period and accumulation of medication may have on persistence with the help of scenario 1 and 2.

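### Carried-over drug stock is credited after the last fill with no cap, and no sensitivity analysis varies accumulation

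*Combined protocol and SAP*

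**What the plan says.** In section 8.2.1, under Time to treatment discontinuation, an episode ends at the date of the last package "plus the number of days that package, as well as accumulated medicine (see more details below), is intended to cover". No cap or expiry is set on the accumulated part. The stated exceptions are a switch and death: "This end date is overruled if there is a new filled prescription of another relevant ATC code or death happens before this".

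The section explains how stock arises. The pharmacy system "allows patients to refill prescriptions when two-thirds of the previous refill has been consumed", so "patients may accumulate large amounts of medication". Patients are therefore "permitted to accumulate medication from overlapping prescriptions and use it to cover future gaps between filled prescriptions", and they become non-persistent "once such a gap exceeds 90 days".

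The text to Figure 1 follows one patient without accumulation (scenario 1) and with it (scenario 2), reaches different end dates, and concludes that "both the definition of grace period and allowing for accumulation of medication will affect persistence". The sentence after that plans a sensitivity analysis of the grace period only, at 60 and 120 days. Section 8.7 adds none on accumulation.

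**The concern.** Two things stand out. First, the purpose given for the stock is to cover gaps between fills, but the end-date rule also adds it after the last fill, where there is no later fill to bridge to. A patient who simply stops is assumed to finish everything in hand first. So is a patient who moves to a hospital-given drug, which section 8.9 says the data do not show. Where leftover drug is not taken, time to treatment discontinuation is overstated.

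Second, the plan identifies accumulation as a driver of persistence and then leaves it fixed. A report showing similar durations at 60, 90 and 120 days could be taken as evidence that the endpoint definition is robust, when half of that definition was never varied. The endpoint concerned is the primary one, in an estimated 1,000 first-line sunitinib patients.

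**Working it through.** **Inputs from section 8.2.1:** grace period 90 days (60 and 120 in sensitivity analyses); refill possible at two-thirds; all stock added after the last fill. **Assumed:** one sunitinib fill covers S = 28 + 14 = 42 days, because the documents give no sunitinib pack size; 13 fills; no long gaps. Refill timing is not given, so a range is shown.

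**The plan's own examples.**
- Refill rule: 2/3 × 3 months = 2 months, which agrees with the example in section 8.2.1.
- Figure 1 contrast, with illustrative fills on days 0, 28 and 170. Without accumulation, supply from the second fill ends on day 28 + 42 = 70. The gap is 170 − 70 = 100 days, more than 90, so the end date is day 70. With accumulation, supply ends on day 84, the gap is 86 days, and the patient continues to day 170 + 42 = 212.

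**Size of the effect with n fills.** With accumulation and no gaps, the end date is nS = 13 × 42 = day 546. Without accumulation it is the last fill date plus 42.

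| Refill timing | Day of 13th fill | End without accumulation | End with accumulation | Difference |
|---|---|---|---|---|
| On time: 42(n − 1) | 504 | 546 | 546 | 0 |
| Two-thirds of the previous refill consumed: 42(n − 2) + 28 | 490 | 532 | 546 | 14 |
| Two-thirds of the time since the last dispensing: 28(n − 1) | 336 | 378 | 546 | 168 |

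In the second row the patient starts each pack only when the previous one is finished, so the stock stays at 14 days. In the third row it grows by 14 days per refill: 14 × 12 = 168. The table counts two-thirds in calendar days, as the plan's example does. Counting in dosing days would raise both non-zero differences, the second to about 23 days (42 − 2/3 × 28 = 23.3).

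**Does the planned sensitivity analysis pick this up?** The grace period only decides whether a later fill is joined to the episode. In all three rows each fill arrives on or before the day the supply runs out, so 60, 90 and 120 days all give day 546.

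**Comparison with the grace-period effect.** In a simulation, switching accumulation off lowered the median duration by 3 to 117 days, and moving the grace period from 60 to 120 days changed it by 0 to 42 days. All of its inputs are assumptions: exponential time on drug with mean 365 days, refills on average 0 to 14 days early, 2% or 5% of refills delayed by up to 150 days, and death or a visible switch soon after stopping in 0 to 80% of patients. It lets stock build up as in the third row. The accumulation effect was smaller than the grace effect when refills were close to on time, similar at about 7 days early, and larger at 14 days early. Truncation reduced it: at 14 days early with 2% delayed refills, from 117 days with no truncation to 51 days with 80% truncated.

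**The case against.** Allowing accumulation is a reasonable, pre-specified base case, its effect is openly illustrated in Figure 1, and section 8.7 describes the study as descriptive. That stands, and it is why the base case should stay. It does not explain why one of two named drivers is left unvaried.

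Four stronger readings are tempting, and the documents do not support them.

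- *The stock is added without limit.* There is no cap, but death or a fill of another listed oral drug cuts the end date, and the two-thirds rule restricts stockpiling.
- *A large part of the endpoint's uncertainty goes untested.* This cannot be shown without refill-timing data. The 168-day figure needs the earliest possible refill every time and a reading by time since dispensing. The wording on consumption of the previous refill supports the 14-day result; the remark about large amounts of medication supports growth. Both readings are open.
- *The 90-day grace period is stretched.* After 8 fills, the time from the end of the last pack's own cover to the next fill could reach 14 × 7 + 90 = 188 days on the extreme reading, or 14 + 90 = 104 days on the consumption reading. However, the plan counts the gap after stock is used up, so time without supply is still at most 90 days.
- *The inflation differs between schedule groups.* Counted by cycle, 28 dosing days cover 42 calendar days on 4:2 (28 + 14) and on 2:1 (2 × 21), so defaulting a patient to 4:2 creates no false stock. A difference would need the 14 or 7 days to be added per fill (42 against 35 days), or a true schedule other than these two.

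**Conclusion.** The point holds as a gap in the sensitivity analyses, not as an arithmetic error. Carried-over stock is added after the last fill with no cap until death or a visible oral switch, and nothing planned shows how much of the reported duration comes from it. With 42 covered days per fill and 13 fills, the contribution is 0, about 14 or up to 168 days before truncation, depending on refill timing and on how the two-thirds rule is read. The documents do not settle where in that range the cohort lies, and they do not show a difference between schedule groups. This is a minor, inexpensive improvement, and the uncertainty about size is itself the reason to run the analysis.

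**What to change.** Keep the base case. Add two sensitivity analyses of time to treatment discontinuation:

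- (a) accumulation switched off, as in Figure 1, scenario 1;
- (b) stock allowed to bridge gaps between fills but not added after the last fill, so that the end date is the last fill plus that package's own cover.

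The two answer different questions. In the illustrative Figure 1 patient, (a) ends on day 70 and (b) on day 212; in the 13-fill patients without gaps they coincide.

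Report the median accumulated days at the end date for each schedule group, which would also show whether the groups differ. Align the two statements in section 8.2.1, so that it is clear whether stock only covers gaps between fills or also extends the end date.

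The cost is two reruns of existing code on data already held, and a wider reported range of duration.

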## **Dosing Schedule**

The different treatment schedules for sunitinib that will be analysed (starting on 4:2, starting on 2:1 and starting on 4:2 and then switching to 2:1) will be defined based on the dosing instruction provided by the prescriber and will be reviewed manually (the variable DOSER in the Swedish Prescribed Drug Register). In the case no instruction is provided at the start of the treatment, a 4:2 dosing scheme (recommended dose in the SPC) will be assumed. When previously supplied dosing instructions cease to be specified, it is assumed that the daily dosage continues in accordance with the previous treatment pattern. A patient is defined as having switched from a 4:2 to a 2:1 schedule if the dosing instruction clearly indicates this. Other sunitinib dosing schedules than the ones described above will not be included in the analysis but will be included in descriptive statistics.

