Another example of study in this area is Bracarda et al (2015) where a retrospective sample of 249 mRCC patients is analysed. The authors found a longer drug survival for patients that moved to a modified 2:1 schedule, both compared to patients that started on a 2:1 schedule and patients that did not modify the dosing scheme. They also found that patients who moved to a 2:1 schedule experienced an improved safety profile compared to during the initial 4:2 schedule [16]. Crumbaker et al (2018) investigated 63 Australian mRCC patients and found that patients starting on a 2:1 dosing schedule had a drug survival that was longer than the overall survival (OS) times seen in the trials using the 4:2 schedule [17]. Boegemann et al (2018) evaluated efficacy and safety regarding sunitinib treatment modification in first line treatment of mRCC and found that in addition to mitigating adverse events (AEs), sunitinib treatment modification may help improve efficacy outcomes by prolonging treatment duration [18].

There is a need for additional research in this area and so far no studies based on Swedish data has been carried out. The current study aims at analyzing sunitinib drug survival and overall survival for Swedish mRCC patients treated in first line, and investigate how these outcomes are affected by different dosing schedules. The study will also investigate axitinib drug survival and overall survival in second line. Safety will not be analysed in this study due to the characteristics of the available data.

Sweden has a unique opportunity in its large number of health data registers run by the National board of Health and Welfare (NBHW). These long-history, high-quality, registers constitute the foundation of a very successful Swedish research tradition in the field of clinical epidemiology, and cover health data in the entire population that is easily

PFIZER CONFIDENTIAL

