## **7. RESEARCH QUESTION AND OBJECTIVES**

The present study is an explorative retrospective study investigating treatment patterns and outcomes for sunitinib and axitinib mRCC patients in a nationwide population-based setting in sweden.

In more detail the primary objective is to:

- Investigate time to treatment discontinuation (treatment duration) for first line treatment with sunitinib for different treatment schedules: 4:2 (4 weeks on/2 weeks off) and 2:1 (2 weeks on/1 week off).

The secondary objectives are to:

- Investigate overall survival (OS) for first line treatment with sunitinib, for different treatment schedules, 4:2 (4 weeks on/2 weeks off) and 2:1 (2 weeks on/1 week off).
- For second line treatment with axitinib, investigate time to treatment discontinuation (treatment duration) and OS.

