## 8. RESEARCH METHODS

### 8.1. Study design

To address the research objectives, the study will be carried out as a national retrospective population-based register study based on data from the NBHW.

Based on the study objectives, the primary endpoint in this study is:

- Time to treatment discontinuation in first line sunitinib patients. Time to event measure from index date to discontinuation of treatment, from 01 July 2005 to 31 December 2019 (assessed from index date up to 180 months). This will be investigated using Kaplan-Meier analysis.

[figure not shown]

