**Table 1. Overview of study variables**

Variable	Role	Data source(s)	Operational definition
Total number of sunitinib 1L patients	Outcome	Prescription Register	Number of sunitinib users with at least one filled prescription (in total and per year over time)
Number of sunitinib 1L 4:2 schedule users	Outcome	Prescription Register	Number of sunitinib users that started on a 4:2 schedule and never had a modification in the schedule (total and per year over time)
Number of sunitinib 1L 2:1 schedule users	Outcome	Prescription Register	Number of sunitinib users that started on a 2:1 schedule and never had a modification in the schedule (total and per year over time)
Number of sunitinib 1L patients that was switched from a 4:2 schedule to a 2:1 schedule	Outcome	Prescription Register	Number of sunitinib users that started on a 4:2 schedule and later was switched to a 2:1 schedule, in total and per year over time

PFIZER CONFIDENTIAL

Total number of axitinib second line patients	Outcome	Prescription Register	Number of axitinib 2L users with at least one filled prescription (in total and per year over time)
Gender	Baseline characteristics	Prescription Register	Male/Female (binary)
Age	Baseline characteristics	Prescription Register	Age will be defined as age at the date of first filled prescription of relevant mRCC medication (continuous; years).
Year of treatment initiation	Baseline characteristics	Prescription Register	Defines the year the treatment was initiated.
Region	Baseline characteristics	Prescription Register	County council of the prescribing physician at first prescription date (categorical), see Table 6 in Annex 3
Time to treatment discontinuation	Outcome	Prescription Register	Time from date of first filled prescription to the end of the prescribed supply, or prescription of other ATC code or death if either of these happen before (details in Section 8.2).
Overall survival	Outcome	Cause of Death Register, Prescription Register	Time from date of first filled prescription of the relevant drug to date of death (number of days) where death is defined as all-cause death; If no date of death is recorded, data is censored at latest available date in data.

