### **8.7. Data analysis**

An overview of the planned analyses are presented in this section. In general, the study is descriptive and does not involve hypothesis testing. Any major modifications of primary endpoint definitions or their analyses would be reflected in a protocol amendment.

Time-to-event analyses will be carried out using standard Kaplan-Meier methods. Kaplan-Meier survival functions will be estimated with relevant events as failure. Time-to-event tables

PFIZER CONFIDENTIAL

and Kaplan-Meier curves will be presented. Log-Rank tests will be used to assess differences across cohorts. In addition, to explore potential determinants of persistence /drug survival and to adjust for differences across cohorts, semi-parametric cox-proportional hazard models will be deployed based on different covariates.

Relevant events for this study include:

- Time to treatment discontinuation
- Death

Time-to-event tables will present:

- Failed/Censored n (%).
- Median time to event.
- 95% confidence intervals of median.
- The 25th and 75th percentiles (q1 and q3).
- Min and max.
- n at risk by unit.
- Time point estimates and 95% Confidence Intervals (CI)by unit.

[figure not shown]
As described in Section 8.2 the analyses will be carried out based on two analysis sets.

Analysis Set 1 consists of all patients indentified with sunitinib as the first line treatment.

Analysis Set 2 consists of all patients indentified with axitinib as the second line treatment.

The Table 4 below displays the output from the time to treatment discontinuation and overall survival analyses that will be carried out based on Analysis Set 1. The output will be presented for three different dosing schemes of interest, patients that started on a 4:2 schedule and that did not switch, patients that started on a 4:2 schedule but later switched to a 2:1 schedule and patients that started on a 2:1 schedule and did not switch. Output will also be presented as Kaplan Meier (KM) curves.

PFIZER CONFIDENTIAL

[figure not shown]

To explore potential determinants drug survival and to adjust for differences across cohorts, semi-parametric cox-proportional hazard models will be deployed based on the following covariates: age, gender, year of treatment initiation, region.

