**Table 5. Time to treatment discontinuation and OS, second line treatment with axitinib**

	L01XE All 2L patients N=xxx
Censored n (%)	xx (xx.x)
Failed n (%)	xx (xx.x)
Survival time (Unit)	
Median (KM)	xx.x
95% CI of median (KM)	xxx.x , xxx.x
Q1, Q3 (KM)	xxx.x , xxx.x
Min, Max	xx.x , xx.x
Kaplan-Meier survival point estimates – n at risk, % (95% CI)	
1 unit	x, x.xx (x.xx,x.xx)
2 unit	x, x.xx (x.xx,x.xx)
.	.
.	.
.	.
n units	x, x.xx (x.xx,x.xx)

PFIZER CONFIDENTIAL

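### First-line sunitinib has no all-patients TTD or OS estimate, and the schedule groups, which are defined inconsistently, appear to drop patients because of later schedule changes

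*Combined protocol and SAP*

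**What the plan says.** Section 8.1 names the primary endpoint as "Time to treatment discontinuation in first line sunitinib patients", with no restriction by schedule. Section 6 gives the aim in similar terms ("The current study aims at analyzing sunitinib drug survival and overall survival for Swedish mRCC patients treated in first line") and then adds how schedules affect these outcomes. Section 7 is narrower. Its primary objective is to "Investigate time to treatment discontinuation (treatment duration) for first line treatment with sunitinib for different treatment schedules", namely 4:2 and 2:1, and the first secondary objective treats OS the same way.

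Section 8.7 states that "Analysis Set 1 consists of all patients indentified with sunitinib as the first line treatment". For that set, however, "The output will be presented for three different dosing schemes of interest": 4:2 without a switch, 4:2 followed by 2:1, and 2:1 without a switch. Table 4 has those three columns only. Table 5, for axitinib, has a column headed "All 2L patients".

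Four places describe the sunitinib groups:
- **Section 8.2.1, Dosing Schedule:** lists starting on 4:2, starting on 2:1, and 4:2 then 2:1, and adds that "Other sunitinib dosing schedules than the ones described above will not be included in the analysis but will be included in descriptive statistics".
- **Section 8.3, Table 1:** the 4:2 group is users who "started on a 4:2 schedule and never had a modification in the schedule". The 2:1 group has the same condition. The switch group has no condition on what follows the switch.
- **Section 8.7, text:** requires no switch in the 4:2 and 2:1 groups, without saying whether any other change counts as a switch.
- **Section 8.7, Table 4:** the third column heading mentions only starting on 2:1.

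**The concern.** There are two linked problems. First, the endpoint as worded in Section 8.1 and the first part of the aim in Section 6 have no matching output. The only planned whole-set result for first-line sunitinib is a patient count in Table 1.

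Second, the three columns need not add up to Analysis Set 1. Under Table 1 and the Dosing Schedule text, patients who change from 4:2 to an unlisted schedule, or who change at all after starting on 2:1, fit no column. Time zero for TTD and OS is the first dispensed package, but this exclusion is decided by something that happens later and only to patients still being dispensed drug. The columns that lose these patients are left with too many early stoppers. If rates of change differ between 4:2 and 2:1 starters, the columns can differ even where schedule has no effect. The planned Cox covariates (age, gender, year of initiation, region) do not address this.

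**Working it through.** **Figure in the plan.** Section 8.5 expects about 1,000 first-line sunitinib patients. It gives no split by schedule, median or rate of schedule change, and Section 8.7 calls the study descriptive. There is therefore no power calculation to reproduce, and the size of the effect can only be illustrated.

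**Who has a column, reading Section 8.2.1 with Table 1**

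| Course | Column |
|---|---|
| 4:2 throughout | 4:2, no switch |
| 4:2, then 2:1 | switch |
| 2:1 throughout | 2:1 |
| 4:2, then an unlisted schedule | none |
| 2:1, then 4:2 or an unlisted schedule | none |
| Unlisted schedule from the start | none |

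The last row is a restriction at baseline and uses no later information. The two rows above it do use later information.

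**Assumptions.** TTD is exponential with hazard λ and an overall median of 9.0 months. A first change to a schedule that leads to exclusion has constant hazard μ, independent of TTD. Schedule has no effect on stopping.

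**Formula.** The share changed before stopping is p = μ/(λ+μ). Patients who stop unchanged have TTD exponential with hazard λ+μ. Their median is ln 2/(λ+μ) = (ln 2/λ) × (1 − p), so it falls by the dropped fraction. Among the dropped patients the survivor function is [exp(−λt) − (1−p)·exp(−λt/(1−p))]/p.

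| Dropped share p (assumed) | Median, remaining column | Median, dropped patients |
|---|---|---|
| 10% | 9.0 × 0.9 = 8.1 | 20.7 |
| 20% | 9.0 × 0.8 = 7.2 | 19.6 |
| 30% | 9.0 × 0.7 = 6.3 | 18.4 |

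**The 4:2 column also loses its switchers to 2:1.** Suppose that 20% of 4:2 starters change first to 2:1 and 10% change first to another schedule. The total hazard is λ/0.7, of which the switch hazard is (0.2/0.7)λ = 0.286λ.
- Removing only the switchers: 9.0/1.286 = 7.0 months.
- Removing the other changers as well: 9.0 × 0.7 = 6.3 months.
- Switch column: 18.4 months if later changers stay, 17.1 if they are removed. It is above 9.0 either way, because a patient must remain on drug until the switch to enter it.
- Excluded from all columns: 10% if switchers who change again are kept, 12.5% if they are not.
- Three columns pooled: 8.2 or 7.9 months on those two readings, so pooling the columns does not recover 9.0.

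**Effect on the contrast.** If 10% of 2:1 starters change and are dropped, their column reads 8.1 months. Against 6.3 in the 4:2 column, the hazard ratio for 4:2 versus 2:1 is (λ/0.7)/(λ/0.9) = 0.9/0.7 = 1.29, with no true schedule effect. Most of the fall in the 4:2 column (9.0 to 7.0) comes from splitting off the switchers. Dropping the other changers accounts for 7.0 to 6.3.

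**The case against.** The strongest reply is that Section 7 controls. The objectives are by schedule, Section 8.1 derives the endpoint from them, and Table 4 answers them. This stands. A reader might infer that the study's primary question goes unanswered or that a pooled estimate should become the headline result, but the documents do not support either. What is missing is an estimate matching the endpoint wording and the general aim.

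A second reply is that exclusion is not certain. Table 1 defines counts, Section 8.7 speaks only of not switching (the one switch that Section 8.2.1 defines is 4:2 to 2:1), and Table 4's third heading has no such condition. This also stands in part. Exclusion from every column is one reading, the one given by Section 8.2.1 with Table 1. The texts allow others, and none removes 4:2-to-2:1 switchers who change again.

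Three further inferences should be resisted. Not all columns are shortened, since the switch column is lengthened. Pooled TTD is not free of schedule coding, because Section 8.2.1 uses the dosing instruction and the off-treatment days to set days covered; only OS is free of it. Patients who start on another schedule do not create the bias.

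Finally, the study is descriptive and the excluded schedules stay in the descriptive statistics. They will be visible there, but no TTD or OS estimate is planned for them.

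**Conclusion.** The point holds in this form. Analysis Set 1 has no all-patients TTD or OS estimate, and the four descriptions of the groups do not agree. Where the never-modified condition is applied, the 4:2 and 2:1 columns are conditioned on the future and their TTD is shortened. OS uses the same time zero and is open to the same conditioning; its size was not calculated.

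The proportional fall in median TTD equals the dropped fraction only under constant hazards with schedule change unrelated to the tendency to stop. If patients who change were already close to stopping, the fall would be smaller. The 9.0-month median and the 10% to 30% range are assumptions, so no figure here predicts the study's results. This is a worthwhile, cheap correction and does not show that the stated objectives cannot be met.

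**What to change.** 1. In Section 8.7 and Table 4, add a column and Kaplan-Meier curve for all of Analysis Set 1, for TTD and OS, alongside the schedule results and not in their place. In Section 8.2.1, state how days covered are derived for patients on other schedules, since the off-treatment adjustment is described only for 4:2 and 2:1.
2. For the 4:2 versus 2:1 starter contrast, keep each patient in the group of the first recorded schedule whatever happens later. Reconcile the group definitions in Section 8.2.1 (Dosing Schedule), Table 1, the text of Section 8.7 and the Table 4 headings, including what counts as a switch and where switchers who change again belong.
3. Optionally, add a descriptive column for other or otherwise modified schedules, so that the groups sum to Analysis Set 1.

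The cost is one or two table columns, a regrouped Kaplan-Meier and Cox run on data already held, one derivation rule and protocol wording. The downside is that the starter contrast then describes a starting strategy, including time after a change, and not continuous use of one schedule.
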